## **8. Roles, responsibilities, and publication**

### **8.1 Roles and Responsibilities**

A team of investigators from the United Kingdom, Asia, Africa, Australia and America are responsible for running this study on behalf of the NIHR Global Health Research Group on Neurotrauma. At each participating unit, there will be a local study team who will conduct local data collection and validation. Local teams may consist of a mix of fully trained surgeons, physicians, trainees, and medical students.

Local collaborators will gain access to their own data upon completion of the study, to compare their practice to international practice. Members of the local study team may request access to a subset of the data to answer a defined research question through post-hoc analyses.

## **9. Support and Funding**

This study has the support of the World Federation of Neurological Societies (WFNS), European Association of Neurosurgical Societies (EANS) and Society of British Neurological Surgeons (SBNS). Funding for the administrative costs of this study are being provided by the National Institute of Health Research (NIHR) Global Health Research Group on Neurotrauma.

## 10. Appendix A – Data Fields

### 10.1 Initial Injury & Admission data

ORION Unique Patient Identifier			
Gender	Male, Female		
Date of Birth	dd/mm/yyyy		
Date/Time of Injury	dd/mm/yyyy HH:MM		
Type of Injury	
 
● Blunt 
 
○ Low energy
 
○ High energy
 
 
 
● Penetrating 
 
○ Low energy
 
○ High energy
 
 
 
		
Mechanism of Injury	
 
            Road Traffic Collision (RTC)           
 
● RTC Pedestrian
 
● RTC Cyclist
 
● RTC Motorcyclist
 
● RTC Motorcyclist (passenger)
 
● RTC Car (driver)
 
● RTC Car (passenger)
 
● RTC other vehicle (driver)
 
● RTC other vehicle (passenger)
 
           Fall           
 
● Fall standing height
 
● Fall from height
 
 	           Assault           
 
● Assault – no weapon
 
● Assault – blunt instrument
 
● Assault – sharp instrument
 
● Assault – firearm
 
           Other           
 
● Self-harm
 
● Other violence
 
● Animal attack
 
● Explosion
 
● Industrial accident (outside categories listed above)
 
● Sport/recreational activity
 
 	
 
	Road Traffic Collision (RTC) 
 
● RTC Pedestrian
 
● RTC Cyclist
 
● RTC Motorcyclist
 
● RTC Motorcyclist (passenger)
 
● RTC Car (driver)
 
● RTC Car (passenger)
 
● RTC other vehicle (driver)
 
● RTC other vehicle (passenger)
 
 Fall 
 
● Fall standing height
 
● Fall from height
 
	Assault 
 
● Assault – no weapon
 
● Assault – blunt instrument
 
● Assault – sharp instrument
 
● Assault – firearm
 
 Other 
 
● Self-harm
 
● Other violence
 
● Animal attack
 
● Explosion
 
● Industrial accident (outside categories listed above)
 
● Sport/recreational activity
 

Road Traffic Collision (RTC) 
 
● RTC Pedestrian
 
● RTC Cyclist
 
● RTC Motorcyclist
 
● RTC Motorcyclist (passenger)
 
● RTC Car (driver)
 
● RTC Car (passenger)
 
● RTC other vehicle (driver)
 
● RTC other vehicle (passenger)
 
 Fall 
 
● Fall standing height
 
● Fall from height
 
	Assault 
 
● Assault – no weapon
 
● Assault – blunt instrument
 
● Assault – sharp instrument
 
● Assault – firearm
 
 Other 
 
● Self-harm
 
● Other violence
 
● Animal attack
 
● Explosion
 
● Industrial accident (outside categories listed above)
 
● Sport/recreational activity
 
		
Date/Time of admission to hospital	dd/mm/yyyy HH:MM		
Was the patient directly transferred from the site of the accident to the current institution?	
 
● Yes
 
● No
 
		
Mode of transport to primary institution	
 
● Air ambulance (helicopter)
 
● Land ambulance (paramedic staffed)
 
● Land ambulance (not paramedic staffed)
 
● Public Transport
 
● Police
 
● Private vehicle
 
● By foot
 
● Other (specify _____)
 
		
Method of transport to the current institution	
 
● Air ambulance (helicopter)
 
● Land ambulance (paramedic staffed)
 
● Land ambulance (not paramedic staffed)
 
● Police
 
● Private vehicle
 
● By foot
 
● Other (specify _____)
 
		
GCS on arrival to your institution (if intubated on arrival, please state pre-intubation GCS)	
 
● Eye Response 
 
○ Open spontaneously - 4
 
○ Open to verbal command - 3
 
○ Open to pain - 2
 
○ No eye opening - 1
 
 
 
● Verbal Response 
 
○ Oriented - 5
 
○ Confused - 4
 
○ Inappropriate words - 3
 
○ Incomprehensible sounds - 2
 
○ No verbal response - 1
 
○ Intubated - T
 
 
 
		

	
 
● Motor Response 
 
○ Obeys commands - 6
 
○ Localising pain - 5
 
○ Withdrawal from pain - 4
 
○ Flexion to pain - 3
 
○ Extension to pain - 2
 
○ No motor response - 1
 
 
 

Kampala Trauma Score	
 
● Age 
 
○ 5-55
 
○ <5 or >55
 
 
 
● SBP (mmHg) 
 
○ >89
 
○ 50-89
 
○ 1-49
 
○ Undetectable
 
 
 
● Respiratory rate (/min) 
 
○ ≤9
 
○ 10-29
 
○ ≥30
 
 
 
● Neurological status 
 
○ Alert
 
○ Responds to verbal stimuli
 
○ Responds to painful stimuli
 
○ Unresponsive
 
 
 
● Serious injuries 
 
○ None
 
○ 1
 
○ 2 or more
 
 
 

Frankel Grade at initial assessment	
 
● A: Complete motor and sensory loss
 
● B: Complete motor loss, incomplete sensory loss
 
● C: Incomplete motor loss without practical use
 
● D: Incomplete motor loss, able to ambulate with or without walking aids
 
● E: Free of neurological symptoms
 

Major intracranial injury (defined as requiring hospital admission in its own)	
 
● Yes
 
● No
 

Site of PRIMARY spinal cord injury	
 
● Occipital condyle to S1:
 
● Unknown
 

Primary vertebral fracture Level	
 
● Occipital condyle to S1:
 
● Unknown
 

Deformity	
 
● Yes
 
● No
 

Any other injury (can select multiple)	
 
● Chest
 
● Abdomen
 
● Pelvis
 
● Long bones
 

Admission location	
 
● General wards
 
● HDU
 
● ITU
 

Admitting Team	
 
● Orthopaedics
 
● Neurosurgery
 
● General Surgery
 
● Medicine
 
● Emergency Department
 

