### 4.2 Data Validation

A number of steps have been taken to ensure validation of all data entered.

- I. The dataset, web-based case report forms, and curation process has been designed according to DAQCOR principles.
- II. Web-based forms in the ORION platform contain fixed options at the point of data entry to maximise the likelihood of accurate and complete data capture at the point of collection.
- III. A local data validator independent to the local study team will be appointed at every participating institution. They will have access to a separate platform on Orion to ensure blinding to the rest of the data collected at their institution. They will be asked to complete a two-phase validation process, with a specific ORION validation user guide available to guide them through the process.
  - a. Prospective Case Acquisition: During the selected 4-week inclusion period, the local data validator will be asked to independently identify and collect all patient cases suitable for inclusion in the study. For validation, they will be required to prospectively collect these cases, recording the admission date, age at admission and AO injury type. This will subsequently be correlated with the data collected by their local team by the central study team.
  - b. Retrospective Operative Data: At 10 weeks from the start of the inclusion period (6-weeks following the end of the inclusion period), the local data validator will be asked to independently access operating theatre logs over the preceding 10 weeks. They will be required to document all the patients who have had an operation for TSI during this period and input the date and type of operation into the validation system where this corresponds to a patient admitted during the inclusion period. This will be used by the central study team to validate this specific cohort of their institution's cases.

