## **5. Statistical Analysis**

Anonymised data will be analysed by the central study team. Fundamentally the main analysis will consist of a quantitative description of case-mix and the variations in processes of care. Identification and description of areas where known best practice is lacking or unavailable will be performed. This will enable identification of potential targets for future implementation studies.

In addition, early outcomes will be assessed to identify case-mix and process factors that may form a substrate for intervention. Participating centres will be stratified based on their country into groups based on their Human Development Index (HDI). The Human Development Index is calculated for each country based on its life expectancy at birth, years of schooling and gross national income (GNI) per capita.

Specifically, after data validation and curation, the primary analysis will comprise of (1) statistical descriptive analysis of patient-level registry variables, (2) characterisation of processes of care using statistical descriptions of both provider profiling data and patient-level process variables followed by a description of typical process groupings. This will follow and extend methodologies that have previously been applied successfully to traumatic brain injury. Case-mix and process analysis will be stratified in a nested way by site, country, and association with human development index (HDI).

Analysis for the secondary objectives will consist of a quantitative statistical summary of non-operative and operative management. Intra- and inter-site variances will be compared and associations with HDI and process of care factors sought.

Whilst only short-term outcomes can be obtained in this pragmatic point-study, outcomes analysis will be attempted for early mortality, functional status as assessed using the 5-point Frankel Grade, neurology, adverse events and trajectory from admission to 6 weeks post-injury (or discharge or death, whichever occurs first). These will be analysed by HDI group in an appropriate nested model accounting for random effects of site and country. Either ordinal models (for statistical power) or dichotomised models will be used depending on the statistical properties of the data and suitability of model assumptions. Mixed effects models will be used to assess the relationship between HDI and deterioration in functional status at 6 weeks while controlling for confounding variables.

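### Neither Frankel item has a 'not assessable' answer, so patients who cannot be examined will carry a guessed or an unexplained missing grade into the trajectory and HDI-deterioration analyses

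*Combined protocol and SAP*

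**What the plan says.** Appendix A, section 10.1, collects "Frankel Grade at initial assessment" with five answers, the last being "E: Free of neurological symptoms". Section 10.5 asks for the grade again at 6 weeks, discharge or death, with the same five answers. Neither item has a code for a patient who cannot be examined, and neither records the date of the examination. Section 4.2 says the web forms "contain fixed options at the point of data entry"; it does not say whether an item may be left blank.

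Section 3.1.2 admits all adults with a first, radiographically confirmed injury and excludes neither intubation nor head injury. Section 10.1 expects such patients. The GCS item adds "if intubated on arrival, please state pre-intubation GCS" and has a verbal code T, the Kampala score includes an unresponsive category, and major intracranial injury is recorded as yes or no. Section 10.5 expects some patients to be on ventilatory support at the end of follow-up.

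Section 5 names the 5-point Frankel grade as the measure of functional status, plans an analysis of trajectory from admission, and states: "Mixed effects models will be used to assess the relationship between HDI and deterioration in functional status at 6 weeks". It gives no list of confounders and no rule for missing or untestable grades.

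**The concern.** A Frankel grade needs a patient who can report sensation and move to command. For a patient who cannot, the form offers only a grade or, if the platform allows it, a blank.

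- **Guessed A** (nothing elicited): the patient starts at the bottom of the scale and cannot deteriorate. If the patient later wakes and moves, the trajectory shows recovery of up to four grades.
- **Guessed E** (no deficit seen): if a real deficit emerges later, it counts as deterioration.
- **Blank**: the baseline is missing, mainly among severely injured patients, with no reason recorded and no planned handling.

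At stake is the HDI comparison of deterioration. Independence in daily living and mobility are collected only at the end of follow-up, so Frankel is the only functional measure with a baseline. The share of patients arriving intubated or sedated, and local coding habits, could plausibly differ between high- and low-HDI centres, though the documents do not show that they do.

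**Working it through.** The documents state no sample size, deterioration rate or share of untestable patients, so there is no plan figure to reproduce. The missing option is established by reading the item lists against section 5. The arithmetic below only shows what size of error could follow.

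**Inputs, all assumed.** u = share untestable at baseline; d = true deterioration among the rest; q = share of the untestable whose later grade is A to D; f = share of the untestable coded E, the remainder being coded A. d and q are the same in both HDI groups unless stated, and every patient is graded correctly at the end. Clustering is ignored.

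**Formula.** Recorded deterioration = (1 − u)d + u·f·q. The second term is false deterioration; patients coded A contribute none.

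**1. Untestable share differs by HDI, same coding habit, true odds ratio 1.00, d = 5%.** For u = 5% v 15%, f = 1, q = 0.3: 0.95×5% + 5%×0.3 = 6.25%, and 0.85×5% + 15%×0.3 = 8.75%. Odds ratio = (0.0875/0.9125)/(0.0625/0.9375) = 1.44. The full set is:

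| u in the two groups | all coded E, q = 0.3 / 0.5 | half E, half A, q = 0.3 / 0.5 | all coded A |
|---|---|---|---|
| 5% v 15% | 1.44 / 1.70 | 1.19 / 1.36 | 0.89 |
| 10% v 20% | 1.37 / 1.55 | 1.18 / 1.31 | 0.88 |

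When all are coded A, the trajectory analysis gains false improvement instead: if 80% later grade B to E, that is 0.8u, or 4% of patients at u = 5% and 12% at u = 15%.

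**2. Share and coding equal in both groups.** Under a true null the odds ratio stays at 1.00. Now let true deterioration be 5% v 8%, an odds ratio of 1.65. With f = 1 and q = 0.3, u = 10% gives 7.5% v 10.2%, odds ratio 1.40; u = 20% gives 10.0% v 12.4%, odds ratio 1.27. The number per group for 80% power (two-sided 0.05) rises from 1059 to 1736 and 2710. With all coded A the odds ratio barely moves (1.65 and 1.64), because the effect is to lose events.

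**3. Share equal, coding differs by HDI; d = 3%, u = 10%, q = 0.4.** Recorded deterioration = 2.7% + 4%×f.

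- f = 0.4 v 0.6: 4.3% v 5.1%, odds ratio 1.20.
- f = 0.25 v 0.75: 3.7% v 5.7%, odds ratio 1.57.
- f = 0 v 1: 2.7% v 6.7%, odds ratio 2.59. This needs every site in one group to code A and every site in the other to code E. The same extreme gives 1.74 at u = 5% and 4.72 at u = 20%.
- If half the untestable patients receive the same guess at both ends and show no change, the f = 1 figure falls to 2.7% + 2.0% = 4.7%, and the extreme odds ratio to about 1.8.

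**The case against.** The strongest reply is that a fixed answer list is not a mandatory field. Appendix A does not reproduce every screen: the AO classification row shows no options, and the procedure item refers to a flow chart on the platform. That stands, so forced guessing cannot be asserted. It does not remove the problem, because an unexplained blank has no planned handling either.

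A clinician might also wait and enter the first reliable grade as the initial one. Section 3.5, however, lists Frankel under presentation on arrival, and with no examination date the analyst could not tell a late grade from an early one.

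Section 5 plans random effects for site and country and adjustment for confounders, and GCS, Kampala neurological status and intracranial injury are all collected. Random effects can absorb part of a site's coding habit, but not error that follows HDI, and none of these variables is named for adjustment. The validator in section 4.2 does not check Frankel.

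That two anatomical items in the same table offer 'Unknown' is weak evidence of an oversight, since most items there do not. The special handling of GCS for intubated patients is better evidence that untestable patients were foreseen.

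A reader might infer that every site must guess and that the HDI model is therefore biased by an odds ratio near 2.6. The documents do not support this. They do not make the field mandatory, they give no rates, and 2.6 contrasts all-A with all-E sites while assuming every such patient is later graded correctly.

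**Conclusion.** The gap is real and nothing else in the documents closes it: both Frankel items lack an answer for a patient who cannot be examined, and two planned analyses depend on them. Whether the result is guessed grades or unexplained missing baselines cannot be settled from the text.

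The size is unknown. With d and q common to the groups, a spurious HDI effect needs the untestable share or the coding habit to differ by HDI. The illustrative range of 0.88 to 1.70 comes from differing shares with common coding; the two partial differences in coding tried gave 1.20 and 1.57. Without such differences the main effect is attenuation, when some patients are coded E, or lost events, when all are coded A.

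The change should be made, but it does not threaten the main analysis, which is descriptive. Confidence is high that the option is missing and much lower about its effect on the HDI model.

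**What to change.** Add 'Not assessable (reason)' to both Frankel items, with an optional first reliable grade and its date. In the deterioration and trajectory models, treat that answer as missing and not as a grade, for example by multiple imputation using GCS, Kampala neurological status and major intracranial injury. Prespecify a sensitivity analysis restricted to patients assessable at baseline, and report the number not assessable by HDI group.

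If the forms are already live, repeat the HDI models excluding, or adjusting for, patients with verbal code T, Kampala neurological status below alert, or major intracranial injury. Motor GCS below 6 should not be used alone, because it may remove testable patients with high cord injury. State that this is an imperfect proxy: pre-intubation GCS is requested, so an intubated patient may be entered with full verbal and motor scores, and sedation is not recorded.

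The cost on the form is one answer with a reason and one optional grade with its date per item. In the analysis, some severely injured patients leave the change models or are imputed (5% to 20% on the shares assumed here). Leaving them out is itself a selection and imputing them rests on a model, so both results should be shown.

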## 2. Overview – Study Flowchart

### **3. Methods**

#### **3.1 Inclusion Criteria**

##### **3.1.1 Centre inclusion Criteria**

Any primary, secondary or tertiary institution worldwide managing patients with TSI is eligible to participate. In many institutions, management for TSI may be provided by spinal surgeons – however, centres in which management for TSI is provided by general surgeons, trauma surgeons, general medical doctors or even non-physician clinicians are also eligible to participate.

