**10.4 Operative Data (If “Yes, performed at this institution” to ‘Was spinal surgery performed?’)**

Grade of most senior surgeon present in the operating theatre	
 
● Fully qualified spinal surgeon
 
● Other qualified surgeon
 
● Surgical trainee
 
● Medical doctor
 

Type of anaesthesia	
 
● General
 
● Local
 
● None
 

Grade of most senior anaesthesia provider present in the operating theatre	
 
● Fully qualified anaesthetist with medical qualification
 
● Anaesthetist in training with medical qualification
 
● Not medically qualified anaesthesia provider
 
● Anaesthetic administered by the surgeon
 

Date of Operation	dd/mm/yyyy
Duration of operation	
 
● Less than 1 hour
 
● 1-5 hours
 
● 5-10 hours
 
● Over 10 hours
 

Were pre-incision prophylactic antibiotics given?	
 
● Yes
 
● No
 

Class of surgical wound	
 
● I Clean
 
● II Clean-contaminated
 
● III Contaminated
 
● IV Dirty-infected
 

Location of surgery	
 
● Cranio-cervical
 
● Cervical
 
● Thoracic
 
● Lumbar
 
● Sacral
 

What was the main procedure undertaken?
 
*If >1 procedure undertaken, refer to the main one
 
** Flow-Chart on ORION Platform **
	
 
● Open 
 
a. Approach: Anterior/Posterior/360
 
b. Minimally invasive surgery? Yes/No
 
c. Open Reduction? Yes/No
 
d. Direct decompression? Yes/No
 
e. In situ fusion? Yes/no
 
f. Fusion? Yes/No 
 
▪ Type of instrumentation 
 
● None
 
● OC
 
● C1/2
 
● Lateral mass
 
● Pedicle
 
● Anterior plating
 
● Bone graft
 
● Intervertebral fusion
 
● Lateral plating
 
 
 
 
 
○ Fluoroscopy used: Yes/No
 
 
 
● Closed 
 
○ Gardener Wells vs Halo
 
○ Mechanism of Maintenance: Collar vs Halo vs Bedrest
 
 
 

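### 'Admitting Team' has no dedicated spinal, trauma surgery or 'Other' option, and the senior-surgeon list has no non-physician or 'Other' option, so part of who delivers care cannot be recorded

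*Combined protocol and SAP*

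**What the plan says.** Section 3.1.1 sets out who may be treating TSI at an eligible centre. In many institutions "management for TSI may be provided by spinal surgeons", and the section then extends eligibility to centres where care is given by "general surgeons, trauma surgeons, general medical doctors or even non-physician clinicians are also eligible to participate".

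Two patient-level fields in Appendix A record who delivers care:

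- **'Admitting Team' (Section 10.1):** "Orthopaedics ● Neurosurgery ● General Surgery ● Medicine ● Emergency Department".
- **Grade of the most senior surgeon in theatre (Section 10.4):** "Fully qualified spinal surgeon ● Other qualified surgeon ● Surgical trainee ● Medical doctor". This section is completed only when spinal surgery was done at the participating institution.

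Neither list has an 'Other' option. Section 4.2 states: "Web-based forms in the ORION platform contain fixed options at the point of data entry". By contrast, the list for the senior anaesthesia provider, also in Section 10.4, includes "Not medically qualified anaesthesia provider".

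**The concern.** The primary objective (Section 1.1) is to describe case-mix and processes of care and how they vary between centres in low and high HDI countries. Section 5 builds the primary analysis on descriptions of the registry variables and on process variables at both provider and patient level. Section 5 also passes process variables on to a later consensus exercise on performance indicators. Which service admits the patient, and who operates, are process variables of this kind.

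If the form has no place for a type of provider that the eligibility rules expect, the tables cannot show it. A descriptive study has no later step that would restore the distinction. The central team holds only anonymised entries and cannot split a coarse code afterwards.

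**Working it through.** No arithmetic applies, because the documents give no sample size or site mix. The check sets each of the five provider types named in Section 3.1.1 against the two lists, which gives 5 × 2 = 10 cells.

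| Provider type (3.1.1) | 'Admitting Team' (10.1) | Senior surgeon (10.4) |
|---|---|---|
| Spinal surgeon | No separate option | Own option |
| General surgeon | Own option | Within 'Other qualified surgeon' |
| Trauma surgeon | No separate option | Within 'Other qualified surgeon' |
| General medical doctor | 'Medicine' | 'Medical doctor' |
| Non-physician clinician | Not comparable: a staff grade, not a department | No option |

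Four cells have an option of their own, two can be recorded but only in a merged category, and one is not a like-for-like comparison. The other three are the gaps: spinal and trauma services under 'Admitting Team', and the non-physician operator under senior surgeon.

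Four further checks bear on whether the gaps matter.

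1. **Is there a way out on the form?** Six other fields in Appendix A offer 'Other (specify)': the two transport fields, specialist therapy, funding, intraoperative complications and discharge destination. These two do not. Section 10.4 has an optional free-text comment on the procedure, but nothing directs operator grade there.
2. **Does another patient-level field fill the gap?** Section 10.4 is blank for patients managed without surgery and for those transferred elsewhere for it. For them 'Admitting Team' is the only field in Appendix A that names the responsible service.
3. **Does provider profiling (Section 3.2) fill it?** It is completed once per institution, before patient-level collection, and its items are not listed. It may show that a site has a spinal service. It would not show which patients that service admitted.
4. **Would validation (Section 4.2) catch it?** The local validator records admission date, age, AO injury type, and date and type of operation. Neither of these two fields is checked.

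**The case against.** The best case against the point has five parts.

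- **Section 3.1.1 is an eligibility statement, not a code list.** 'Admitting Team' lists departments. A spinal unit that sits within orthopaedics or neurosurgery is recorded correctly, only less finely. A patient seen by a non-physician clinician under Medicine or the Emergency Department is also correctly placed. This stands. It confines the first gap to services outside the five departments, plus a loss of detail for units within them. It is also a reason not to add a staff grade to a list of departments.
- **The senior-surgeon list is fuller than it may seem.** A reader might infer that neither list can record spinal or trauma surgeons. The documents do not support that: the list opens with a fully qualified spinal surgeon, and a trauma surgeon fits 'Other qualified surgeon', with only the subtype lost.
- **Intensive care is not lost.** 'Admitting Team' has no such option, but 'Admission location' in Section 10.1 offers HDU and ITU, and Section 10.5 collects ICU admission and dates. This stands too.
- **No planned analysis names either field.** True, but Section 5 plans a description of the registry variables in general, and these two are among them.
- **The data set was refined with clinicians from both settings (Section 3.3), and a pilot is planned (Section 4.1).** The pilot is a natural place to find the gap. The lists as they stand still have it.

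**Conclusion.** The point holds in a limited form. 'Admitting Team' cannot separate a stand-alone spinal or trauma service from orthopaedics, neurosurgery or general surgery. The senior-surgeon list cannot show a non-physician operator, so the recorded number is zero by construction, whatever the true number. Both gaps limit the patient-level description of who delivers care. No sample size, error rate or outcome definition is affected.

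The size cannot be given. It depends on how many sites have such services or operators, and the documents do not say. Section 3.1.1 says that non-physician clinicians may manage TSI; it does not say that they perform spinal surgery.

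A reader might go on to infer that most entries at some sites will be wrong, or that the errors gather at the best- and worst-resourced sites. The documents support neither. A nearest-category entry is often coarse rather than wrong. They do not say whether the fields are mandatory, so a site might leave one blank. A concentration by resource level would require the unknown site mix.

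**What to change.** In Section 10.1, add 'Spinal surgery (dedicated service)', 'Trauma surgery' and 'Other (specify)' to 'Admitting Team'. In Section 10.4, add 'Not medically qualified provider', to match the anaesthesia list, and 'Other (specify)' to the senior-surgeon list. The existing options stay as they are, so entries can still be collapsed to the present categories where a coarser table is wanted.

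The cost is five extra options across two drop-down lists, and some central work to code the free-text 'Other' entries, which will come from many countries.
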